### 12.2.1 Protocol

The Investigator indicated on FDA Form 1572 will act as the Principal Investigator at each study site. Protocols will be noted as approved by placement of the Novum Representative's signature on the cover page. The Sponsor of the study will also approve the protocol by having a study-responsible individual sign the protocol cover page. The Principal Investigator will sign the protocol signature page indicating their agreement to conduct the study according to the protocol.

### 12.2.2 Informed Consent

An ICF that includes all of the relevant elements currently required by FDA, ICH, and local state regulations will be provided to each prospective study patient before enrollment into the study. The type and method of study, tests to be administered, any potential or possible hazards, and the patient's right to withdraw from the study at any time will be explained to the patients by the Investigator or designee. Once the Investigator or designee is assured that an individual candidate understands the implications of participating in this study, the patient will be asked to give consent by signing and dating in the appropriate areas of the ICF. The Investigator or designee will also sign and date the form, along with a staff member who will sign the ICF as a witness to verify that the patient has indeed received information. If any other language is required, translation will be performed by a certified translator. A copy of the ICF will be provided to the patient. For patients who are considered minors in the state the study is being conducted (< 18 years in most states) the parent or legal guardian should sign the consent form and the child will be required to sign a patient "assent" form, as appropriate. Patients 11-17 years of age will read and sign an IRB-approved assent form and patients 6-10 years of age will provide verbal assent. Patients 2-5 years of age will be exempt from providing assent based on the child's comprehension and cognitive skills.

### 12.2.3 Protocol and Informed Consent Changes

Sponsor approved changes to the protocol or the ICF will be implemented as revisions to the original documents and will require additional review and approval by the IRB. Revisions to the original protocol will be documented in amendments, incorporated as a preface to the new version. Any revision that substantially alters the study design or increases potential risk to the patient requires the patient's consent to continue in the study. The approvals will be processed in accordance with the established IRB procedures. Copies of all protocol and ICF amendments/revisions, along with letters noting IRB approval, will be submitted to the Sponsor.

### 12.2.4 Source Documents and Electronic Case Report Forms (eCRF)

All patients will be identified by initials, date of birth and a unique patient number. Source documents will be used to record all study-related data. Source document entries will be used to complete eCRFs. A set of eCRFs will be completed for each patient randomized in the study. All data and eCRFs will be reviewed, evaluated and signed by the Investigator.

The original source documents and a copy of the corresponding eCRFs will be retained by the Investigator. Patients who terminate early from the study will have the Visit 3 (End of Study) source/eCRF completed.

## CONFIDENTIAL PROTOCOL

A Randomized, Double-Blind, Parallel-Design, Multiple-Site Study to Evaluate the Therapeutic Equivalence of Permethrin Cream, 5% (Encube Ethicals) Compared to Elimite™ Cream (permethrin) 5% (Prestium Pharma, Inc.) in the Treatment of Scabies

---

### 12.2.5 Drug Accountability

All study product receipt, inventory, dispensing, dosing and reconciliation records will be maintained in compliance with federal regulations. The study product will be dispensed to qualified study patients according to established procedures. At the end of the study (after the database has been locked) all used and unused study product will be returned to Sponsor or designee.

### 12.2.6 Drug Storage

Study product will be stored at controlled room temperature 20-25°C (68-77°F) [USP Controlled Room Temperature] in a secure place with access by authorized individuals only. The Investigator will be responsible for maintaining accurate records of drug receipt, dispensing, and return. After finalizing the study report, all partially used and unused study product will be returned to Sponsor or designee.

### 12.2.7 Retention of Reserve Samples

For every study product shipment received at the Investigator site, the Investigator (or designee) will randomly select at least one block of study product for retention, unless otherwise instructed by the Sponsor and/or Novum. These retention samples should be stored under the appropriate storage conditions for a minimum of 5 years following the application approval or, if not approved, at least 5 years after the completion of the study. Retention samples should not be returned to Sponsor/CRO/packaging group at any time.

### 12.2.8 Pregnancies

Patients with a positive pregnancy test during screening will not be enrolled in the study. Patients who report that they have become pregnant during the study or have a positive pregnancy test at Visit 3 will be followed to completion of the pregnancy. The pregnancy will be reported as an AE.

Female patients of childbearing potential must have been using and must agree to continue to use accepted methods of birth control, throughout the study. Acceptable methods of birth control include total abstinence, intrauterine device, a double-barrier method (such as condom with spermicide or diaphragm with spermicide), oral, transdermal, injected, or implanted non-hormonal or hormonal contraceptive throughout the study. Female patients using hormonal contraceptives should have been on the same product/dosing regimen for at least 28 days before Visit 1 and should not change this regimen during the study. A sterile sexual partner is not considered an adequate form of birth control. Before study enrollment women of childbearing potential must be advised of the importance of avoiding pregnancy during study participation.

A negative result of a urine pregnancy test having a minimum sensitivity of at least 50 mIU/mL for human chorionic gonadotropin (hCG) should be obtained, before study participation. Pregnancy testing will be performed at Visits 1 and 3 and the results of all pregnancy tests (positive or negative) will be documented.

## CONFIDENTIAL PROTOCOL

A Randomized, Double-Blind, Parallel-Design, Multiple-Site Study to Evaluate the Therapeutic Equivalence of Permethrin Cream, 5% (Encube Ethicals) Compared to Elimate™ Cream (permethrin) 5% (Prestium Pharma, Inc.) in the Treatment of Scabies

---

If following initiation of study treatment, it is subsequently discovered that a study patient is pregnant or may have been pregnant at the time of study product exposure, the study product will be permanently discontinued. The Principal Investigator or designee must immediately notify the Medical Monitor of this event. Reporting timelines and Novum/Sponsor contact will be consistent with SAE reporting guidelines (i.e., pregnancies will be reported to the Sponsor/Novum within 24 hours to the contacts listed in section 10.8.2).

Protocol-required procedures for study discontinuation and follow-up must be performed on the patient. Other appropriate pregnancy follow-up procedures should be considered if indicated. All follow-up information regarding the course of the pregnancy, including perinatal and neonatal outcome will be communicated as per the above guidelines. Infants should be followed for a minimum of eight weeks after birth.

### **12.2.9 Reporting Safety Information to the IRB**

The Investigator must promptly report to the Investigator's IRB all unanticipated problems involving risks to patients. This includes death from any cause and all SAEs occurring during the study, regardless of the assessed causality.

### **12.2.10 Record Retention**

All drug accountability records, eCRFs, source data and related regulatory documents must be retained for at least two years following completion of the study or Test product approval for marketing by the FDA.

### **12.2.11 Study Monitoring and Auditing**

Novum will be responsible for monitoring the study according to GCP and applicable regulations. Monitoring visits are for the purpose of confirming adherence to the protocol and to verify complete and accurate data collection. The clinical site will make all records associated with the study available to Novum's representative during such visits and audits.

The study may be subject to audit by the Sponsor, Sponsor Representative or by regulatory authorities. If such an audit occurs the Investigator must agree to allow access to required patient records. By signing this protocol, the Investigator grants permission to personnel from the Sponsor, its representatives and appropriate regulatory authorities for on-site monitoring of all appropriate study documentation, as well as on-site review of study procedures.

### **12.2.12 End of the Trial**

The end of the trial is defined as the time at which the last patient has completed their last visit in the study. Upon completion of the study, the study product will no longer be available to the patient but the Investigator can, at their discretion, discuss alternative treatments with the patient.

### **12.2.13 Clinical Study Report**

At the end of the study a full report per requirements of Sponsor and regulatory authorities will be prepared which will include a narrative of the clinical conduct and results of the study, a statistical report including a description of the analysis performed, and other documentation as

## **CONFIDENTIAL PROTOCOL**

A Randomized, Double-Blind, Parallel-Design, Multiple-Site Study to Evaluate the Therapeutic Equivalence of Permethrin Cream, 5% (Encube Ethicals) Compared to Elimite™ Cream (permethrin) 5% (Prestium Pharma, Inc.) in the Treatment of Scabies

---

may be appropriate. The report will be in electronic format according to eCTD and ICH formatting standards and guidelines.

## CONFIDENTIAL PROTOCOL

A Randomized, Double-Blind, Parallel-Design, Multiple-Site Study to Evaluate the Therapeutic Equivalence of Permethrin Cream, 5% (Encube Ethicals) Compared to Elimate™ Cream (permethrin) 5% (Prestium Pharma, Inc.) in the Treatment of Scabies

---

## **CONFIDENTIAL PROTOCOL**

A Randomized, Double-Blind, Parallel-Design, Multiple-Site Study to Evaluate the Therapeutic Equivalence of Permethrin Cream, 5% (Encube Ethicals) Compared to Elimite™ Cream (permethrin) 5% (Prestium Pharma, Inc.) in the Treatment of Scabies

---

### **14.0 APPENDICES**

#### **14.1 APPENDIX A: RATING OF SCABIES SIGNS AND SYMPTOMS**

##### PRURITUS

At each clinic visit, patients will be asked to rate the severity of pruritus (overall itch intensity and effect of itching on nighttime sleep) on the following 4-point scale.

0 = none (complete absence of itching)

1 = mild (slight itching, no sleep loss)

2 = moderate (definitely present, interrupts sleep)

3 = severe (marked, intense, cannot sleep)

##### LESION COUNT

At each clinic visit, the lesion count will be evaluated and rated as follows:

< 50 = mild

50-100 = moderate

> 100 = severe

## **CONFIDENTIAL PROTOCOL**

A Randomized, Double-Blind, Parallel-Design, Multiple-Site Study to Evaluate the Therapeutic Equivalence of Permethrin Cream, 5% (Encube Ethicals) Compared to Elimite™ Cream (permethrin) 5% (Prestium Pharma, Inc.) in the Treatment of Scabies

---

### **14.2 APPENDIX B: DERMOSCOPY AND MICROSCOPY FOR SCABIES DIAGNOSIS**

#### **SKIN SCRAPING/MICROSCOPY**

Skin scrapings will be obtained with a sterile scalpel after the application of 1 drop of mineral oil onto the lesion. The scraped material will be transferred to a slide and covered with a cover slip. Reading is to be performed immediately under a microscope, or within 3 hours, at 40 X magnification. The number of scraped sites until the examination is declared negative will be left to the recognition of the attending Investigator in relation to the clinical picture.

A single scraping is not considered sufficient to adequately define parasitological cure.

The best efforts should be made to attempt valid skin scrapings for microscopic examinations, even in case of virtually healed lesions as appropriate.

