### 10.5.3 Visit 3 (Day 28 ± 4): End of Study or Early Termination

1. **Vital Signs:** Record Patient's blood pressure, pulse, temperature and respiration rate.
2. **Adverse Events:** Patients will be questioned about any health status changes/AEs since last visit. All AEs will be recorded.
3. **Concomitant Medication:** Review the patient's use of any new or ongoing concomitant medications since the last visit.
4. **Microscopic Examination:** Skin scrapings will be taken to record microscopic evidence of scabies mites/eggs/feces in the skin. Refer to Appendix B.
5. **Scabies Signs and Symptoms Rating (pruritus, lesion count):** Patients will be asked to complete a rating scale to record symptom severity of nocturnal itching. Investigators will be

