### 10.6.6 Microscopic Examination

At each clinic visit, the Investigator will conduct a dermatological examination to identify living mites in the skin. A dermoscope can be used (but is not required) to observe lesions/papules/blisters/burrows on the skin. Once determined that the lesions are characteristic of scabies, the Investigator will collect a skin scraping sample for identification of living mites/eggs/feces by light microscopy. See Appendix B for details.

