Patients will be instructed to self-administer a single dose of study product or, if patient is a child, then parent/guardian will apply study product to him/her on Day 1 according to the dosing instructions provided. A second application may be required if presence of scabies infestation is microscopically demonstrated (i.e., living mites, viable mite eggs, or mite fecal matter present) at Visit 2. The second dose will be self-administered by the patient or if patient is a child, then parent/guardian will apply study product to him/her at Visit 2. Eligible household members and close contacts of the patient will be offered permethrin cream (if they are in need of treatment) as a method to reduce cross-contamination within a household. Additionally, household members will be requested to follow the standard hygiene practices. Patients whose household members are not willing to comply with the standard of care for Scabies management (i.e., use of generic permethrin cream and standard hygiene practices) will not be enrolled in the study.

During the study, patients will visit the clinical center for a total of three scheduled visits:

- Visit 1 (Day 1): Screening/Baseline
- Visit 2 (Day 14 ± 4): Interim Visit
- Visit 3 (Day 28 ± 4): End of Study or Early Termination

Final assessments will be carried out at Visit 3 (Day 28 ± 4), which is the test-of-cure visit. The test-of-cure visit will occur 4 weeks (± 4 days) after the end of the single application treatment on study Day 1 or 2 weeks (± 4 days) after the end of a second application, if necessary, on study Visit 2. Therapeutic cure of scabies will be evaluated based on microscopic evidence of absence of scabies infestation (i.e., no living mites, no viable mite eggs, and no mite fecal matter), visual evidence of absence of new lesions and healing of original lesions, regardless of the presence of post-scabetic nodules (i.e., post-scabetic nodules need not be considered as new lesions or persistence of old lesions). The primary statistical analysis of interest is the proportion of patients in each treatment group with therapeutic cure (parasitological cure plus clinical cure) of scabies.

**NOVUM PHARMACEUTICAL RESEARCH SERVICES
STATISTICAL ANALYSIS PLAN**

Permethrin Cream, 5%

Protocol / Study No. 71675502

Figure 1 Study Schematic

	Visit 1 Screening/Baseline (Day 1)	Visit 2 Interim Visit (Day 14 ± 4)	Visit 3 (Day 28 ± 4) End of Study or Early Termination
Informed Consent	X		

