6. STUDY ENDPOINT

The primary efficacy endpoint is the proportion of patients in each treatment group with Therapeutic Cure (parasitological cure plus clinical cure) of scabies at the test-of-cure visit

**NOVUM PHARMACEUTICAL RESEARCH SERVICES
STATISTICAL ANALYSIS PLAN**

Permethrin Cream, 5%

Protocol / Study No. 71675502

conducted at Day 28 ± 4. A parasitological cure is defined as failure to demonstrate microscopically the presence of scabies infestation (i.e., no living mites, no viable mite eggs, and no mite fecal matter present). A clinical cure is defined as visual evidence of absence of new lesions and healing of original lesions, regardless the presence of post-scabietic nodules (i.e., post-scabietic nodules need not be considered as new lesions or persistence of old lesions).

Patients who do not respond to the initial treatment and have new lesions or microscopic confirmation of mites, ova, or fecal matter on Day 14 ± 4 will be treated as treatment failure in the final analysis on Day 28.

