7. STUDY POPULATIONS

Per-Protocol (PP) Population

The PP population will include:

- Met the inclusion/exclusion criteria as defined in this protocol at Visit 1.
- Did not take any prohibited medications throughout the study.
- Did not have any significant deviations from the protocol. Did not develop any concurrent dermatological condition or illness exhibiting symptoms similar to scabies, or symptoms that in the Investigator's opinion would interfere with endpoint assessments.
- Completed the last study visit (Visit 3) Day 28 ± 4.

Patients will be included in the PP population as treatment failures in the final analysis on Day 28 (provided they had no significant protocol deviations) if they 1) withdrew from the study because of lack of efficacy, 2) show therapeutic cure at Day 14 ± 4 but re-infestation at Day 28 ± 4, or 3) do not respond to the initial treatment and have new lesions or microscopic confirmation of mites, ova, or fecal matter on Day 14 ± 4.

Safety Population

The safety population will include all patients who are randomized who applied at least one dose of the assigned study product.

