9. TABLE, LISTING AND FIGURE SHELLS

The following shells are provided in order to provide a framework for the display of data from this study. These shells may not be reflective of every aspect of this study but are intended to show the general layout of the Tables, Listings and Figures that will be included in the final clinical study report. Tables, Listings and Figures are numbered following the ICH structure. Table headers, variables names and footnotes will be modified as needed following data analyses. All descriptive and inferential statistical analyses will be performed using SAS[®] statistical software Version 9.4 or higher, unless otherwise noted.

TABLE, LISTING AND FIGURE SHELLS

Programming note:

Put Program Name in the footnote where it is stored, Location of Output stored, and Date and time when the output is generated.

T14.1.1 Summary of Patient's Disposition

Patients Randomized	Test N = xxx n (%)	Reference N = xxx n (%)	Total N = xxx n (%)
Completed Study	xxx (xx.x)	xxx (xx.x)	xxx (xx.x)
Terminated Early	xxx (xx.x)	xxx (xx.x)	xxx (xx.x)
Adverse Event	xxx (xx.x)	xxx (xx.x)	xxx (xx.x)
Lack of efficacy	xxx (xx.x)	xxx (xx.x)	xxx (xx.x)
Protocol Deviation	xxx (xx.x)	xxx (xx.x)	xxx (xx.x)
Pregnancy	xxx (xx.x)	xxx (xx.x)	xxx (xx.x)
etc.			
Other	xxx (xx.x)	xxx (xx.x)	xxx (xx.x)

Test: Permethrin Cream, 5%, (Encube Ethicals)

Reference: Elimate™ Cream (permethrin) 5% (Prestium Pharma, Inc.)

N= number of patients randomized in that particular group; n= number of patient with data available for that particular group;

total % is based on N

PROGRAM: L:\DEV\755\71675502\SAS\PGM\XXXX
 Created on: ddmmmyy hh:mm

OUTPUT: L:\DEV\755\71675502\SAS\OUT\XXXX
 Page 1 of N

T14.1.2 Summary of Protocol Deviations

	Test N = xxx n (%)	Reference N = xxx n (%)	Total N = xxx n (%)
Total Patients with Protocol Deviations	xxx (xx.x)	xxx (xx.x)	xxx (xx.x)
Total Deviations	xxx	xxx	xxx
Lost to Follow-up	xxx	xxx	xxx
Missed Visit	xxx	xxx	xxx
Non-compliance with dosing requirements	xxx	xxx	xxx
Outside Visit Window	xxx	xxx	xxx
Restricted Medication Use	xxx	xxx	xxx
Randomized in Error	xxx	xxx	xxx
Other	xxx	xxx	xxx

Test: Permethrin Cream, 5%, (Encube Ethicals)

Reference: Elimite™ Cream (permethrin) 5% (Prestium Pharma, Inc.)

N= number of patients randomized in that particular group; n= number of patient with data available for that particular group;
total % is based on N

PROGRAM: L:\DEV\755\71675502\SAS\PGM\XXXX
Created on: ddmmmyy hh:mm

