Reference: Elimite™ Cream (permethrin) 5% (Prestium Pharma, Inc.)

*Treatment compliance will be calculated based off the following criteria: 1.) all patients randomized will have at least 1 dose, confirmed from the study drug administration form via the eCRF. Date of first and last dose and total confirmed doses applied will confirm treatment use. 2.) A patient who is required to dose a second time, compliance will be calculated using criteria 1 and the following data points (via the eCRF) positive microscopic result at Visit 2 and selection of “yes” regarding the question “based on your assessment and microscopic results, is continued treatment required?”

PROGRAM: L:\DEV\755\71675502\SAS\PGM\XXXX
Created on: ddmmmyy hh:mm

OUTPUT: L:\DEV\755\71675502\SAS\OUT\XXXX
Page 1 of N

L16.2.6.1 Listing of Scabies Signs and Symptoms Rating and Microscopic Evaluation of Scabies

Treatment Group	Patient Randomization Number	Visit	Scabies Lesion Count	Are there any new lesions present?	Have all original lesions healed?	Number of scraped sites	Microscopic Examination Result	Clinical Cure	Parasitological Cure	Therapeutic Cure
Test	xxxx	1	Moderate	NA	NA	3	Positive (mites, eggs)			
		2	Mild	No	No	3	Positive (eggs)			
		3	Mild	No	Yes	NA	0	Negative	Yes	Yes
	xxxx	1	Moderate	NA	NA	3	Positive (eggs)			
		2	Mild	No	No	3	Positive (eggs)			
		3	Mild	Yes	Yes	0	Negative	No	Yes	No

Reference

Test: Permethrin Cream, 5%, (Encube Ethicals)
Reference: Elimite™ Cream (permethrin) 5% (Prestium Pharma, Inc.)

PROGRAM: L:\DEV\755\71675502\SAS\PGM\XXXX
Created on: ddmmmyy hh:mm

OUTPUT: L:\DEV\755\71675502\SAS\OUT\XXXX
Page 1 of N

L16.2.6.2 Listing of Patient Pruritus Assessment

Treatment Group	Patient Randomization Number	Visit 1	Visit 2	Visit 3 / Early Termination	No Itch Persistence
Test	xxxx	1 (Mild) 2 (Moderate)	1 (Mild) 1 (Mild)	0 (None) 1 (Mild)	Yes No

Reference

Test: Permethrin Cream, 5%, (Encube Ethicals)
Reference: Elimite™ Cream (permethrin) 5% (Prestium Pharma, Inc.)

PROGRAM: L:\DEV\755\71675502\SAS\PGM\XXXX
Created on: ddmmmyy hh:mm

OUTPUT: L:\DEV\755\71675502\SAS\OUT\XXXX
Page 1 of N

L16.2.6.3 Listing of Investigator Evaluator Initials On Scabies Signs & Symptoms Rating

Treatment Group	Patient Randomization Number	Visit 1	Visit 2	Visit 3 / Early Termination
Test	xxxx	XYZ	D-G	D-G

Reference

Test: Permethrin Cream, 5%, (Encube Ethicals)
Reference: Elimite™ Cream (permethrin) 5% (Prestium Pharma, Inc.)

PROGRAM: L:\DEV\755\71675502\SAS\PGM\XXXX

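### Does the SAP need its own rule for parasitological cure when no site, or only one, was scraped at Visit 3?

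*Protocol*

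**What the plan says.** Appendix B of the protocol (Skin Scraping/Microscopy) tells the Investigator that "A single scraping is not considered sufficient to adequately define parasitological cure". It leaves the number of sites needed for a negative finding to the Investigator's judgement and asks for valid scrapings to be attempted even when lesions have almost healed.

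SAP 6 states that "A parasitological cure is defined as failure to demonstrate microscopically the presence of scabies infestation". Protocol 11.5 uses the same definition. Neither mentions a number of sites or refers to Appendix B. SAP 3 and Protocol 10.1 word it differently: "Therapeutic cure of scabies will be evaluated based on microscopic evidence of absence of scabies infestation".

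On whether scraping happens at all, Protocol 10.5.3 says of Visit 3 that "Skin scrapings will be taken to record microscopic evidence of scabies mites/eggs/feces in the skin", and the schedule in Protocol 6.0 marks a microscopic examination at all three visits. Protocol 10.6.6 adds: "Once determined that the lesions are characteristic of scabies, the Investigator will collect a skin scraping sample".

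The site count is recorded. Shell T14.1.6 summarises it by arm and visit, and L16.2.6.1 lists it for each patient beside the microscopy result and the cure status.

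**The concern.** Therapeutic Cure needs both clinical and parasitological cure. In a patient whose skin has healed, microscopy is the only part of the endpoint that can still show failure at Visit 3. If cure means only that nothing was demonstrated, a patient who was never scraped could pass. Protocol 10.6.6 can be read as scraping only where lesions look typical, which would make a Visit 3 with no scraped site foreseeable in healed patients.

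The shell "L16.2.6.1 Listing of Scabies Signs and Symptoms Rating and Microscopic Evaluation of Scabies" seems to confirm this. Its second example patient has 0 scraped sites at Visit 3, a result of Negative and Parasitological Cure marked Yes.

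In an equivalence trial this error runs in the unsafe direction. If a share *m* of failures is missed in both arms, a true difference of −20 points is seen as −20 × (1 − *m*), so the arms look more alike than they are. T14.1.6 gives the mean, median and range of sites but not how many patients had 0 or 1.

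**Working it through.** **1. What happens if the plan is followed.** Protocol 10.5.3 and the schedule call for microscopy at Visit 3, and Appendix B extends the effort to nearly healed lesions. A Visit 3 without scrapings is therefore a departure from the protocol. SAP 7 admits to the per-protocol population only patients without significant deviations, and T14.1.3.1 has a row for major protocol deviations. The randomization schedule reaches the statistician only after database lock (SAP 4), so such cases can be classified blind.

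**2. Whether the two cure wordings conflict.** Both are followed by the same explanation: no living mites, no viable eggs, no fecal matter. Both presuppose that someone looked down a microscope. A patient with no examination meets the SAP 6 wording only on a strained reading.

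**3. What the shell shows.** SAP 9 says of its shells: "These shells may not be reflective of every aspect of this study but are intended to show the general layout". The second example patient was egg-positive at Visit 2 and has new lesions at Visit 3, so is a failure whatever the microscopy says. The values are plainly placeholders: the next shell, L16.2.6.2, shows an example patient with a baseline itch score of 1, which inclusion criterion 6 does not allow.

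**4. Who could be misclassified.** SAP 7 already counts as failures those who "do not respond to the initial treatment and have new lesions or microscopic confirmation of mites, ova, or fecal matter" at Day 14. What remains is a patient not failed at Day 14, with healed skin at Visit 3, still infested, and scraped at no site or too few. Protocol 8.3 expects little re-infestation between the two visits.

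**5. Reproducing the plan's figure.** Inputs from SAP 5: cure 88% and 83%, 107 per arm, margin ±20 points, 90% interval with Yates' correction.
- se = √(0.83 × 0.17/107 + 0.88 × 0.12/107) = 0.0480; correction 1/107 = 0.0093.
- Power = Φ((0.20 − 0.0093 − 0.05)/0.0480 − 1.645) + Φ((0.20 − 0.0093 + 0.05)/0.0480 − 1.645) − 1 = 0.900, which agrees with the stated 90%.
- Under the uncorrected interval that SAP 8.2.1 specifies, exact binomial power at 107 per arm is 92.9%.

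**6. Size of the bias.** Exact binomial enumeration of the SAP 8.2.1 rule, 107 per arm, true cure 68% (Test) and 88% (Reference), that is, on the margin. If a share *m* of all failures is missed in each arm, the apparent cure rates are 1 − 0.32(1 − *m*) and 1 − 0.12(1 − *m*). The expected number of hidden failures is 107 × (0.32 + 0.12) × *m*. Every *m* is an assumption.

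| *m* | Hidden failures in 214 | False equivalence |
|---|---|---|
| 0 | 0 | 5.1% |
| 1% | 0.5 | 5.5% |
| 2.5% | 1.2 | 6.2% |
| 5% | 2.4 | 7.4% |
| 10% | 4.7 | 10.6% |

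*m* is the share of failures that could be hidden in this way times the share of those actually missed. For example, 25% × 10% = 2.5%.

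**7. What the alternative codings would do.** If a share *s* of cures is recoded as non-cure in both arms, both rates are multiplied by (1 − *s*):

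| *s* | False equivalence (68% v 88%) | Power (83% v 88%) |
|---|---|---|
| 0 | 5.1% | 92.9% |
| 2% | 5.9% | 91.2% |
| 5% | 7.0% | 88.6% |
| 10% | 9.3% | 85.0% |

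Excluding patients, if unrelated to outcome, gives 5.2% and 91.6% at 102 per arm, and 5.3% and 90.3% at 96 per arm.

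**The case for a change.** The strongest reply is that the safeguard in step 1 is incomplete. The documents do not define a significant deviation, the LOCF sensitivity analysis covers only patients with no post-dose data, and SAP 8.5 has no rule for an absent scraping. The choice could also move a result. With 89/107 cures on Test and 94/107 on Reference, the 90% interval runs from −12.6% to +3.2%. Recoding 7 Test cures alone takes the lower limit to −19.7%, and recoding 8 takes it to −20.7%, outside the margin.

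Part of this stands: no sentence names the case of 0 or 1 site. But the example recodes one arm only, in a double-blind trial, and is a worst case rather than an expectation. For 0 sites, an analyst has no microscopy result to count, and the sensible reading is that the examination was not done. For 1 site, the objection needs a single scraping to mean a single site. Appendix B uses both terms without equating them and leaves the number of sites to the Investigator. Overriding an Investigator's negative reading from one site would in effect impose a two-site minimum that the protocol chose not to set.

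The reporting complaint is weak. L16.2.6.1 already lists site count, result and cure status by patient and arm, so patients with 0 or 1 site can be counted from it.

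**Conclusion.** The observation is accurate: neither Protocol 11.5 nor SAP 6 carries over Appendix B's warning, and the mock row in L16.2.6.1 sits badly with it. It is a missing detail that analysts can fill from the rest of the plan, together with a clerical slip in a layout shell. If the protocol is followed, the case should seldom arise; if it does, the deviation rule is available and the data to see it are listed.

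The effect is probably small: false equivalence of 5.5% to 6.2% instead of 5.1% if 1% to 2.5% of failures are missed equally in both arms. It would reach 10.6% only if one failure in ten were hidden, which is hard to square with so narrow a group. These figures rest on assumed shares, and the documents cannot show the true frequency. Writing in a non-cure rule would bring its own inflation (5.9% to 9.3%) and cost power (down to 85.0%), so it is not clearly safer. According to Protocol 8.3 the last visit was on October 30, 2017, the day before Amendment 1, so no rewording can alter how patients were scraped. No change to the plan is called for.
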